10.6 Power and Type-I Error Simulations

The operating characteristics of this trial were determined through trial simulation. We hypothesized several scenarios for the underlying rates for the effectiveness and safety endpoints, and simulated the entire trial multiple times under each scenario. In each virtual trial, the interim analysis was conducted according to the pre-specified rules, and results were tracked for each trial, including whether the trial was successful on each endpoint individually and on both endpoints, whether trial success was achieved early, etc. Three different enrollment schedules were considered for the simulations corresponding to realistic, slow, and fast enrollment schedules based on logistical considerations:

Table 1. Assumed enrollment rates

	Expected number of patients per month																	
	1	2	3	4	5	6	7	8	9	10	11	12	13	14	15	16	17	18
Realistic	7.5	10.5	13.5	7.5	15	18	24	30	30	30	30	30	30	30	24			
Slow	7.2	7.2	7.2	9.6	7.2	16.8	22.8	24	24	24	24	24	24	24	24	24	24	12
Fast	10.2	10.2	5.1	10.2	11.9	15.3	17	25.5	32.3	34	34	34	34	34	23.8			

10.6 1 Effectiveness Outcome

In order to simulate the effectiveness outcome for a virtual subject, we need to simulate whether the subject has a failure and when that failure occurs. As previously discussed in section 5, a piecewise exponential time-to-failure model is assumed and calibrated to have a particular failure rate $(1 - p_E)$ at the end of follow-up. The profiles are constructed by taking advantage of the relationship:

$$p_E = \exp(-[2h_1 + (8 - 2)h_2 + (39 - 8)h_3]),$$

where p_E is the failure-free rate at 12 months. Rates from a previous study were assumed and calibrated to simulate effectiveness outcomes. From ThermoCool SSED, the reported hazard rates have the following pattern:

$$h_1 = (38.06)h_3;$$

$$h_2 = (1.71)h_3;$$

$$h_3 = (1)h_3.$$

To simulate data, we used the above multiplicative factors from ThermoCool and then found the value for h_3 , such that when multiplied by each of the assumed rates for the three time intervals, the failure-free rate at 12 months (39 weeks following 13 weeks blanking period) matches the desired scenarios. Table 2 shows the derived hazard rates that were used to simulate data for a range of assumed failure-free rates.

Table 2. Parameters to generate failure times

Failure-free Rate	Hazard Rate (h)		
	h_1	h_2	h_3
0.50	0.2248	0.0101	0.0059
0.60	0.1656	0.0074	0.0044
0.62	0.1550	0.0070	0.0041
0.65	0.1397	0.0063	0.0037
0.70	0.1157	0.0052	0.0030
0.99999	0.0001	0.0001	0.0001

10.6.2 Attrition Rate Profile

For each subject, a time-to-withdrawal is simulated from an exponential distribution with a 5% dropout rate for the safety outcome and a 15% dropout rate for the effectiveness outcome. Both dropout rates are per year of follow-up. If a subject experiences a failure prior to their withdrawal time, then their outcome is recorded as a failure. A subject is censored at the time of withdrawal if the simulated withdrawal time is prior to the simulated failure time.

10.6.3 Simulation Results

Table 3.a provides the estimated powers for various effectiveness rates assuming a true safety rate of 7% under the realistic enrollment scenario. The power for each effectiveness rate scenario is obtained based on 10,000 simulations. The table also provides the proportion of times we expect to stop enrollment at the interim look for adequate sample size, and the proportion of times early success is achieved. Assuming a true effectiveness rates of 62 to 70%, the power for the effectiveness endpoint is estimated to be greater than 80%. When we assume the true safety rate of 7%, the powers for the safety endpoint are over 85% across all effectiveness rate scenarios. Thus, the trial is adequately powered for various assumed effectiveness rates.

Table 3.a Estimated power for various effectiveness rates assuming a true safety rate of 7% using 10,000 simulations for each scenario

Safety Rate	Effectiveness Rate	Overall Power	Win Effect	Win Safety	N=180	N=255	N=330	Early Success
0.07	0.60	0.6749	0.7289	0.9149	0.3702	0.2191	0.4107	0.6202
	0.62	0.7764	0.8527	0.9026	0.4272	0.2653	0.3075	0.7436
	0.65	0.8395	0.9457	0.8853	0.5535	0.2854	0.1611	0.8316
	0.70	0.8550	0.9954	0.8588	0.7296	0.2357	0.0347	0.8547

Table 3.b shows Type I error rates for the trial under the worst-case scenarios using the realistic enrollment scenario; (1) Assuming the true effectiveness rate is on the decision boundary of 50% and the device is to be safe (the true safety rate of 0.001%); and (2) Assuming the true PAE rate is on the decision boundary of 14% and the device is to be effective (the true effectiveness rate is 99.999%). Since the primary safety analysis is performed at a 2.5% level Type-I error and the sample size is selected independent of the safety endpoint, the Type-I error for the safety hypothesis is controlled at 2.5% and is confirmed in Table 1.b (see the safety rate of 14% and effectiveness rate of 99.999%). For the worst-case scenario for the effectiveness endpoint, Table 1.b shows that the estimated Type-I error rate from the simulation trials was 1.68%, still below the 2.5% threshold.

Table 3.b Estimated Type-I error for the worst-case scenarios based on 25,000 simulations

Safety Rate	Effectiveness Rate	Type-I error	95% C.I
0.14	0.99999	0.0172	[0.0156 , 0.0189]
0.00001	0.50	0.0168	[0.0152 , 0.0185]

Table 3.c provides the proportion of times we would stop the trial at each interim for futility under the realistic enrollment scenario.

Table 3.c Proportion of times the trial will stop at each interim for futility on 10,000 simulations for each scenario

Safety Rate	Effectiveness Rate	Overall Futility	N=180	N=255
0.07	0.60	0.0034	0.0020	0.0014
	0.62	0.0012	0.0008	0.0004
	0.65	0.0003	0.0003	0.0000

	0.70	0.0001	0.0001	0.0000
--	------	--------	--------	--------

Tables 4.a, 4.c, 5.a, and 5.c provide the estimated power and futility proportions under the slow and fast scenarios. Tables 4.b and 5.b provide the estimated type-I errors under the slow and fast scenarios.

Table 4.a Estimated power for slow enrollment assumption based on 10,000 simulations

Safety Rate	Effectiveness Rate	Overall Power	Win Effect	Win Safety	N=180	N=255	N=330	Early Success
0.07	0.60	0.6758	0.7377	0.9085	0.3768	0.2621	0.3611	0.6410
	0.62	0.7769	0.8624	0.8975	0.4711	0.3021	0.2268	0.7595
	0.65	0.8336	0.9469	0.8788	0.6111	0.2949	0.0940	0.8307
	0.70	0.8399	0.9956	0.8437	0.8121	0.1782	0.0097	0.8399

Table 4.b Estimated Type-I error for slow enrollment assumption based on 25,000 simulations

Safety Rate	Effectiveness Rate	Type-I error	95% C.I
0.14	0.99999	0.0182	[0.0166 , 0.0199]
0.00001	0.50	0.0167	[0.0151 , 0.0184]

Table 4.c Proportion of times the trial will stop at each interim for futility for slow enrollment assumption based on 10,000 simulations

Safety Rate	Effectiveness Rate	Overall Futility	N=180	N=255
0.07	0.60	0.0037	0.0023	0.0014
	0.62	0.0011	0.0009	0.0002
	0.65	0.0002	0.0002	0.0000
	0.70	0.0000	0.0000	0.0000

Table 5.a Estimated power for fast enrollment assumption based on 10,000 simulations

Safety Rate	Effectiveness Rate	Power	Win Effect	Win Safety	N=180	N=255	N=330	Early Success
0.07	0.60	0.6777	0.7284	0.9212	0.3584	0.2110	0.4306	0.5995
	0.62	0.7702	0.8439	0.9059	0.4316	0.2460	0.3224	0.7223
	0.65	0.8407	0.9459	0.8863	0.5641	0.2576	0.1783	0.8315
	0.70	0.8499	0.9953	0.8540	0.7604	0.1972	0.0424	0.8493

Table 5.b Estimated Type-I error for fast enrollment assumption based on 25,000 simulations

Safety Rate	Effectiveness Rate	Type-I error	95% C.I
0.14	0.99999	0.0172	[0.0156 , 0.0189]

0.00001	0.50	0.0159	[0.0144 , 0.0175]
---------	------	--------	-------------------

Table 5.c Proportion of times the trial will stop at each interim for futility for fast enrollment assumption based on 10,000 simulations

Safety Rate	Effectiveness Rate	Overall Futility	N=180	N=255
0.07	0.60	0.0034	0.0024	0.0010
	0.62	0.0019	0.0014	0.0005
	0.65	0.0003	0.0003	0.0000
	0.70	0.0001	0.0001	0.0000

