7.4.1.1 Early Success Interim Analysis of Primary Safety Endpoint

The primary safety outcome for all subjects will be known at the time of the interim analysis and will be used for hypothesis testing. Notably, primary adverse events only occur within a 3-month window of the procedure by definition (with the exception of a procedure or device related death, pulmonary vein stenosis, and atrio-esophageal fistula) which will result in nearly identical hypothesis tests at the interim and final analyses.

At the time of the early success interim analysis, the primary safety endpoint will be met if:

$$\Pr(p_s < 0.14 | y, n) > 0.975$$

where p_s is the PAE rate. A beta-binomial model with a non-informative uniform prior Beta (1,1) will be used for the safety rate. If the posterior probability of the safety rate being less than 14% is greater than 0.975 then the study will be considered to have demonstrated safety of the device at the early success interim analysis.

To investigate the robustness of the analysis result, the following sensitivity analyses will be performed in the FAS and mITT analysis sets unless otherwise noted at the time of the early success interim analysis with available data:

- **Sensitivity to Analysis Set**

The primary safety endpoint will be analyzed in the FAS as a sensitivity analysis.

- **Snap-Shot Binomial Analysis**

The number and percentage of subjects with primary safety events will be presented along with one-sided 97.5% exact binomial upper confidence bounds. Subjects with missing outcomes will be excluded from the analysis. Missing outcomes of primary safety endpoints is defined in Section 7.4.3.

- **Best-case Scenario**

The point estimate for the PAE rate will be estimated by treating subjects with missing primary safety outcomes as free from primary safety events.

- **Worst-case Scenario**

The point estimate for the PAE rate will be estimated by treating subjects with missing primary safety outcomes as failures.

- **Tipping Point Analysis**

Tipping point analysis will be performed for the primary safety endpoint to assess the impact of missing outcomes on the safety conclusion. The posterior distribution will be updated each time treating a subject with a missing outcome as failure to evaluate whether a tipping point is identified.

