7.4.2.1 Early Success Interim Analysis of Primary Effectiveness Endpoint

At the time of the early success interim analysis, the primary effectiveness endpoint will be met if:

$$\Pr(p_E > 0.50 | x, n) > 0.9975$$

where p_E is the effectiveness success rate. If the posterior probability of the effectiveness success rate being greater than 50% is greater than 0.9975 then the study will be considered to have demonstrated effectiveness of the device at the early success interim analysis.

At the time of the early success interim analysis, the time-to-failure during the 9-month (39 weeks) post-blanking period will be modeled by using a piecewise exponential model. The model will consist of three distinct time intervals during the 9-month evaluation period: (0, 2], (2, 8], and (8, 39] weeks. Failure times during each time interval is assumed to be exponentially distributed with a different hazard rate in each segment. The model is:

$$f(t) = \exp(-th(t))$$

where

$$h(t) = \begin{cases} \lambda_1 & 0 < t \leq 2 \\ \lambda_2 & 2 < t \leq 8 \\ \lambda_3 & 8 < t \leq 39 \end{cases}$$

Vague Gamma prior distributions will be assumed for λ_1 , λ_2 , and λ_3 . Given hazard rates λ_1 , λ_2 , and λ_3 , the failure-free rate at 12 months (9 months post-blanking) p_E can then be estimated

by

$$p_E = \exp(-[2\lambda_1 + (8 - 2)\lambda_2 + (39 - 8)\lambda_3])$$

At the interim, the total number of primary effectiveness events and the total subject exposure time will be used to update the vague Gamma prior and obtain the posterior Gamma distribution for each segment. Then 10,000 random hazard rates will be sampled from the posterior distribution for each segment and each triplet set of hazard rates will be used to calculate p_E . The distribution of p_E is estimated based on the 10,000 calculated p_E s. If the probability of p_E being greater than 50% is greater than 0.9975 (99.75%), the trial will declare early success.

To investigate the robustness of the analysis result, the following sensitivity analyses will be performed in the mITT and PP analysis sets at the time of the early success interim analysis with the available data:

- **Sensitivity to Analysis Set**

The primary effectiveness endpoint will be analyzed in the mITT analysis set as a sensitivity analysis.

- **Kaplan-Meier Analysis**

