7.4.2.2 Final Analysis of Primary Effectiveness Endpoint

If trial success is not declared at the early success interim, the final analysis for the primary effectiveness endpoint will use a beta-binomial model with a non-informative uniform prior Beta (1,1) based on complete 12-month follow-up data. At the time of the final analysis, the primary effectiveness endpoint will be considered as success if:

$$\Pr(p_E > 0.50|x, n) > 0.9775$$

where p_E is the 12-month effectiveness success rate. If the posterior probability of the effectiveness rate being greater than 50% is greater than 0.9775 then the study will be considered to have demonstrated effectiveness of the device.

To investigate the robustness of the analysis result, the following sensitivity analyses will be performed in the mITT and PP analysis sets unless otherwise noted at the time of the final effectiveness analysis:

- **Sensitivity to Analysis Set**

The primary effectiveness endpoint will be analyzed in the mITT analysis set as a sensitivity analysis.

- **Snap-Shot Binomial Analysis**

Number and percentage of subjects free from primary effectiveness failure will be presented along with one-sided 97.75% exact binomial lower confidence bounds. Subjects with missing outcomes will be excluded from this analysis. Missing outcomes of primary effectiveness endpoints is defined in Section 7.4.3.

- **Kaplan-Meier Analysis**

Kaplan-Meier estimates and plots will be used to characterize the time to first primary effectiveness event, including acute procedural failure and documented symptomatic/asymptomatic AF, AT, or AFL recurrence following the initial ablation procedure. This will provide a non-parametric estimate of the primary effectiveness endpoint. The Kaplan-Meier analysis will account for all follow-up time for all subjects in the analysis set. Subjects with incomplete follow-up who remain failure free will be censored at the time of last observation. The probability of freedom from primary effectiveness failure at each monthly timepoint post blanking will be presented along with the one-sided 97.75% lower confidence bound using Greenwood's variance.

- **Best-case Scenario**

The point estimate for freedom from primary effectiveness failure will be estimated by treating subjects with missing primary effectiveness outcomes as free from primary effectiveness events.

- **Worst-case Scenario**

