10.4 Interim Analyses for Early Success

One interim analysis is planned for an early success claim. The interim analysis will be performed when the first 30 subjects complete full follow-up of one year and all subjects in the MITT analysis set complete 3 months of follow-up. For the safety endpoint, the outcome for all patients will be known at the time of this interim analysis and the test will be final primary safety analysis.

At the interim analysis, the trial will declare early success if:

1. The safety objective is met.
2. Posterior probability of the effectiveness proportion p_E being greater than 50% is greater than 0.9975.

The posterior probability is estimated based on the proposed model in the next section.

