10.5 Modeling for Effectiveness

For the effectiveness endpoint, the time-to-failure during the 9-month (39 weeks) post-blanking period is modeled by using a piecewise exponential model. The model has three distinct time intervals: (0, 2], (2, 8], and (8, 39] weeks. These intervals are based on a model fit to the ThermoCool Pivotal trial and the SmartTouch IDE trial. The three-piece exponential model

provides a reasonable amount of flexibility in capturing the functional form of the survival function for the effectiveness endpoint.

For the model-based approach, failure times during each interval is assumed to be exponentially distributed, with different hazard rates in each segment. The model is:

$$f(t) = \exp(-th(t)),$$

where

$$h(t) = \begin{cases} h_1 & 0 < t \leq 2; \\ h_2 & 2 < t \leq 8; \\ h_3 & 8 < t \leq 39. \end{cases}$$

A vague Gamma(1, 1) prior distribution will be used for each h in the model. Given hazard rates h_1, h_2 , and h_3 , the failure-free rate at 12 months p_E can then be estimated by $p_E = \exp(-[2h_1 + (8 - 2)h_2 + (39 - 8)h_3])$.

At the time of the early success interim analysis, the total number of primary effectiveness events and the total subject exposure time will be used to update the vague Gamma prior and obtain the posterior Gamma distribution for each segment. Then 10,000 random hazard rates will be sampled from the posterior distribution for each segment and each triplet set of hazard rates will be used to calculate p_E . The distribution of p_E is estimated based on the 10,000 calculated p_E s. If the probability of p_E being greater than 50% is greater than 0.9975(99.75%), the trial will declare early success.

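### The simulated early-success, power and Type I error figures in SAP (Wave II) Appendix I are not jointly reproducible under the stated 0.9975 early-success rule

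*SAP*

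**What the plan says.** The early effectiveness cut is the same wherever it appears. SAP (Wave II) 10.4 requires: "Posterior probability of the effectiveness proportion p_E being greater than 50% is greater than 0.9975". SAP 7.4.2.1 has "If the posterior probability of the effectiveness success rate being greater than 50% is greater than 0.9975", and protocol 20.4.4.2 and SAP 10.5 agree. The Kaplan-Meier sensitivity analysis in SAP 7.4.2.1 uses a matching one-sided 99.75% bound.

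The final test is looser (SAP 7.4.2.2): "If the posterior probability of the effectiveness rate being greater than 50% is greater than 0.9775". Safety must also be met at the early look (SAP 7.4.1.1): "If the posterior probability of the safety rate being less than 14% is greater than 0.975". That look waits until 30 subjects have one year of follow-up and "all subjects in the MITT analysis set complete 3 months of follow-up" (SAP 10.4).

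For the early model, SAP 10.5 says: "A vague Gamma(1, 1) prior distribution will be used for each h in the model". SAP 10.3.1 uses Gamma(0.1, 0.1) for the predictive probabilities, and SAP 7.4.2.1 names only a vague Gamma.

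SAP 10.6 says each virtual trial followed the pre-specified rules. SAP 10.6.3 then reports power, the proportion stopping enrolment at each look, "and the proportion of times early success is achieved". For a true PAE rate of 7% and true effectiveness of 60, 62, 65 and 70%, Table 3.a gives early success of 0.6202, 0.7436, 0.8316 and 0.8547, and overall power of 0.6749, 0.7764, 0.8395 and 0.8550. At a true effectiveness of 50%, "the estimated Type-I error rate from the simulation trials was 1.68%, still below the 2.5% threshold" (SAP 10.6.3).

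**The concern.** The tables look odd before any simulation. Early success divided by overall power is 0.6202/0.6749 = 92% at 60%, 0.7436/0.7764 = 96% at 62%, 0.8316/0.8395 = 99% at 65% and 0.8547/0.8550 = 100% at 70%. Nearly every success is therefore declared on partial follow-up at 0.9975, leaving almost nothing for the easier 0.9775 test on full follow-up. At a true rate of 60%, a much stricter cut applied to less data should not behave that way.

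Appendix I is the only evidence offered that this pair of thresholds gives the claimed operating characteristics. If the simulation used another rule, the documents do not show how the stated one performs. The figure most affected would be the chance of an early claim.

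**Working it through.** **Inputs** (SAP (Wave II) Appendix I unless noted)
- Realistic accrual (Table 1): 7.5, 10.5, 13.5, 7.5, 15, 18, 24, then 30 for seven months, then 24; total 330.
- Hazard ratios 38.06 : 1.71 : 1 over 2, 6 and 31 weeks, after 13 weeks of blanking (10.6.1).
- Exponential withdrawal, 15% per year for effectiveness and 5% for safety (10.6.2).
- Looks at 180 and 255, maximum 330. Enrolment stops if predictive probability exceeds 90% at the current N or is below 2.5% at 330 (10.3).
- An imputed drop-out is not an event in the predictive step (10.3.1). Event-free withdrawals are excluded from the final analysis (SAP 7.4.3).
- Assumption: exposure is in weeks. Both stated priors were run in the early model.

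**Step 1. Hazards.** h3 = -ln(p_E) / (2×38.06 + 6×1.71 + 31) = -ln(p_E) / 117.38. At 65%: 0.4308/117.38 = 0.0037, so h1 = 0.1397 and h2 = 0.0063. These match Table 2.

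**Step 2. Rule.** In interval j, h_j ~ Gamma(a + events, b + exposure), and p_E = exp(-[2h1 + 6h2 + 31h3]), with 10,000 draws. Early success needs Pr(p_E > 0.50) > 0.9975 and Pr(p_S < 0.14) > 0.975, the latter from Beta(1+y, 1+n-y). The look falls at the later of last enrolment plus 3 months and 30 subjects reaching 12 months: about month 15.0, 15.4 and 17.9 for N = 180, 255 and 330.

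**Step 3. Does the machinery reproduce the rest?** With imputed drop-outs as non-events, the N split at 65% is 0.59/0.29/0.13 (withdrawal clock from day 0) or 0.50/0.32/0.18 (clock from day 91). The stated 0.5535/0.2854/0.1611 lies between them. The safety win is 0.88-0.89 (stated 0.8853).

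**Step 4. Early success on both endpoints.** Ranges cover separately coded runs, the withdrawal clock and the timing of the look. Cells used from several hundred to 12,000 trials; with 2,000 the standard error is about 0.01.

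| True rate | Stated | 0.9975, Gamma(1,1) | 0.9975, Gamma(0.1,0.1) | 0.9775, Gamma(1,1) | 0.99, Gamma(0.1,0.1) |
|---|---|---|---|---|---|
| 60% | 0.6202 | 0.27-0.33 | 0.41-0.46 | 0.60-0.66 | 0.622 |
| 62% | 0.7436 | 0.43-0.51 | 0.57-0.63 | 0.74-0.78 | 0.743 |
| 65% | 0.8316 | 0.63-0.70 | 0.75-0.79 | 0.82-0.86 | 0.835 |
| 70% | 0.8547 | 0.83 | 0.85 | 0.857 | 0.857 |
| 50%: Type I error | 1.68% | 0.3-0.4% | 0.4-0.7% | 1.1-1.5% | - |

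Gamma(1,1) at 0.975 also comes close: 0.616 at 60%, 0.828-0.838 at 65% and Type I error 1.66% with the clock from day 0. The gap is not noise. With 25,000 simulations the standard error of 1.68% is √(0.0168×0.9832/25,000) = 0.08 percentage points.

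**Step 5. Other schedules.** At 65% and 0.9975 with Gamma(1,1), slow enrolment gives 0.65-0.66 (stated 0.8307) and fast enrolment 0.66 (stated 0.8315).

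**Step 6. Power at 0.9975.** At 60%, overall power is 0.58-0.64 (stated 0.6749); the upper end is 0.6903×0.924 = 0.638. At 62% it is 0.73 to 0.79 (0.8690×0.909 = 0.790), which straddles the stated 0.7764. At 65% it is 0.84-0.86 (stated 0.8395).

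**The case against.** The strongest reply is that the SAP leaves coding choices open and that some of them bring single cells close to the tables at 0.9975.
- **Withdrawals excluded in the predictive step.** Early success at 65% rises to about 0.77-0.84. But the N split becomes 0.36/0.24/0.41, the 60% row reaches only 0.38-0.53, and Type I error is 0.3-0.5%.
- **No drop-out.** Type I error is about 2.1%, not far from 1.68%, so the Type I mismatch alone does not identify the threshold. But the effectiveness win at 60% is then 0.92 (stated 0.7289).
- **Withdrawals excluded and event time run from enrolment, ignoring the 13-week blanking offset.** This gives 0.86/0.88 at 65%, 0.55/0.65 at 60% and an N split at 65% of 0.55/0.26/0.19. It still misses the 60% N split and the Type I error, and it departs from SAP 10.6.1.
- **Withdrawals counted as successes in the final test.** Type I error is about 4.2% and the effectiveness win at 60% is 0.94. Neither matches.

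So a reader should not infer that 0.83 at 65% is unattainable at 0.9975. It is attainable in isolation, at the cost of the other columns. Nor should a reader infer that 0.9775 was the programmed cut: several threshold and prior pairs fit about equally well, and the documents do not say.

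The objection also limits the consequences. The decision rule itself is unambiguous. The protocol synopsis says only that CE filing follows if the early criteria are met; nothing is said to rest on the simulated probability.

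**Conclusion.** The stated rule and the reported operating characteristics do not belong together. On the withdrawal handling that best reproduces the N split, the early-success column is too high by 4-20 points at 65% (0.83 minus 0.79 to 0.63) and by 16-35 points at 60% (0.62 minus 0.46 to 0.27). The stated Type I error of 1.68% is more than twice what the rule gives. Power at 60% is overstated by about 4-9 points. At 62% the power difference runs from about 5 points to none, so that row needs a re-run more than it shows an error.

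A reader might infer that the trial is underpowered or that its error rate is not controlled. The documents do not support this. Under 0.9975, power at the design assumption of 65%/7% stays above 80%, and Type I error stays below 2.5% provided event-free withdrawals are excluded from the final analysis, as SAP 7.4.3 says.

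The result rests on exposure in weeks, Table 1 accrual and exponential attrition. That the tables reflect a looser cut is an inference from fit.

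Protocol 20.2 needs correction in any case. It gives Type I errors of 0.0191 and 0.0145 beside intervals of (0.0156, 0.0189) and (0.0152, 0.0185), which exclude them. SAP Table 3.b prints the same intervals around 0.0172 and 0.0168.

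**What to change.** Before any interim data are seen:
1. Re-run Tables 3-5 at 0.9975 with one named prior for the early model and one stated handling of withdrawals in the predictive step, the early look and the final test. Name that prior in SAP 7.4.2.1 as well.
2. Restate early success, power and Type I error in SAP Appendix I, and the two Type I errors with their intervals in protocol 20.2. SAP section 6 and protocol 20.2 give no early-success or 60-62% power figures, so nothing of that kind needs changing there.
3. If another early threshold was intended, reconcile it in protocol 20.4.4.2 and SAP 7.4.2.1, 10.4 and 10.5, including the 99.75% Kaplan-Meier bound, and show that Type I error stays below 2.5%. This is not automatic: Gamma(0.1,0.1) at 0.9775 gives about 2.7-2.9%.

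The cost is a simulation re-run, a document update and less favourable early-success figures. If 0.9975 stands, trial conduct does not change.
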